### **9.5.2. Safety Analyses**

Safety analysis will be conducted using the safety population and summarized by treatment group. The treatment-emergent period will be defined as the period from initial exposure of the study drug through 48 weeks after treatment administration or the date of the initiation of another investigational agent or surgical intervention, whichever occurs first. Safety will be assessed through summaries of adverse events and clinical laboratory evaluations.

AEs will be coded using the latest version of Medical Dictionary for Regulatory Activities (MedDRA; version 21.0 or higher). All reported AEs (whether treatment emergent or not) will be included in by-patient AE listings. The severity of all adverse events will be evaluated by the investigator. The incidence of the adverse events will be presented by system organ class and preferred term, relationship to study treatment, and severity. Treatment emergent AESIs and treatment related AESIs will also be summarized by system organ class (SOC) and preferred term (PT). A list of all AESIs can be found in [Section 8.5.6](#).

Laboratory data will consist of chemistry, hematology, and urinalysis data. Only data collected by the laboratory will be included in the analysis.

Descriptive statistics of observed values and change from baseline for vital signs and post void residual volume will be listed and summarized.

Supplemental safety analyses will be performed to separate subjects that did or did not receive additional OAB treatment at or after Week 24. Tables that are to be repeated with the alternative safety population will be described further in the SAP.

### **9.6. Multiplicity**

All efficacy endpoints will be considered descriptive and no multiplicity adjustments will be performed for these endpoints.

## 9.7. Subgroup Analyses

Subgroup analyses of endpoints may be conducted. Additional details of any planned subgroup analyses will be provided in the SAP.

## 9.8. Planned Analyses

### 9.8.1. Interim Analyses

Two or more interim analyses may be conducted; when  $\geq 50\%$  of subjects in Cohort 1, and/or when  $\geq 50\%$  of subjects in Cohort 2 have completed at least 12 weeks of follow-up post-randomization (or prematurely exited the study prior to Week 12). Any interim analysis performed is for future planning purposes.

The planned interim analysis will be conducted to evaluate the objectives of the protocol at Week 12. These analyses will be performed after the completion of the following steps:

- All subjects in Cohorts 1 and 2 have completed Week 12 (or prematurely exited the study prior to Week 12)
- All required database cleaning activities have been completed and final database release and freeze has been declared by data management
- All criteria for unblinding the randomization code have been met.

For any interim analysis, the subject and the investigator or delegate(s) who are involved in the treatment or clinical evaluation of the subjects will remain blinded to the treatment assignments. Limited personnel from the Sponsor will be unblinded (double-blind, sponsor-open design). Sponsor personnel who are directly involved with site interactions and communications (eg, study data manager and site monitors) will remain blinded to subject level treatment assignment.

### 9.8.2. Final Analyses

The planned final end-of-study analysis will be performed once the final clinical database lock (after all subjects complete the study or exit the study prematurely) has been achieved and treatment codes have been unblinded to the statistics and programming team. The clinical study report will be based on final analysis results.

### 9.8.3. Data and Safety Monitoring Board

A DSMB will be retained to assess, on an ongoing basis, all safety aspects of this study including unblinded review of safety data after all subjects reach Week 6 (or prematurely exited the study prior to Week 6) in Cohort 1 (URO-902 24 mg). Randomization into Cohort 2 will begin only after the DSMB has recommended it is safe to proceed. This committee will be an external independent DSMB that monitors safety. The detailed activities including meeting plans will be

described and documented in the DSMB Charter. A separate statistical analysis plan may be prepared for the DSMB.

## **10. SUPPORTING DOCUMENTATION AND OPERATIONAL CONSIDERATIONS**

### **10.1. Appendix 1: Regulatory, Ethical, and Study Oversight Considerations**

#### **10.1.1. Regulatory and Ethical Considerations**

- This study will be conducted in accordance with the protocol and with the following:
  - Consensus ethical principles derived from international guidelines including the Declaration of Helsinki and Council for International Organizations of Medical Sciences (CIOMS) International Ethical Guidelines
  - Applicable International Conference on Harmonisation of Technical Requirements for Registration of Pharmaceuticals for Human Use (ICH)/International Organization for Standardization Good Clinical Practice (GCP) guidelines
  - Applicable laws and regulations
- The protocol, protocol amendments, ICF, Investigator's Brochure, and other relevant documents (eg, subject-oriented materials) must be submitted to an IRB/IEC by the investigator and reviewed and approved by the IRB/IEC before the study is initiated.
- Any amendments to the protocol will require IRB/IEC approval before implementation of changes made to the study design, except for changes necessary to eliminate an immediate hazard to study subjects.
- The investigator will be responsible for the following:
  - Providing written summaries of the status of the study to the IRB/IEC annually or more frequently in accordance with the requirements, policies, and procedures established by the IRB/IEC
  - Notifying the IRB/IEC of SAEs or other significant safety findings as required by IRB/IEC procedures
  - Providing oversight of the overall conduct of the study at the site and adherence to requirements of applicable local regulations, for example 21 Code of Federal Regulations (CFR), ICH guidelines, the IRB/IEC, and European regulation 536/2014 for clinical studies (if applicable)

#### **10.1.2. Financial Disclosure**

Investigators and subinvestigators will provide the Sponsor or designee with sufficient, accurate financial information as requested to allow the Sponsor or designee to submit complete and accurate financial certification or disclosure statements to the appropriate regulatory authorities. Investigators are responsible for providing information on financial interests during the course of the study and for 1 year after completion of the study.

### **10.1.3. Informed Consent Process**

- The investigator or his/her representative will explain the nature of the study to the subject or her legally authorized representative and answer all questions regarding the study.
- Subjects must be informed that their participation is voluntary. Subjects or their legally authorized representatives will be required to sign a statement of informed consent that meets the requirements of 21 CFR 50, local regulations, ICH guidelines, Health Insurance Portability and Accountability Act requirements, where applicable, and the IRB/IEC or study center.
- The medical record must include a statement that written informed consent was obtained before the subject was enrolled in the study and the date the written consent was obtained. The authorized person obtaining the informed consent must also sign the ICF.
- Subjects must be re-consented to the most current version of the ICF(s) during their participation in the study.
- A copy of the ICF(s) must be provided to the subject or the subject's legally authorized representative.
- Subjects who are rescreened are required to sign a new ICF.

### **10.1.4. Data Protection**

- Subjects will be assigned a unique identifier. Any subject records or datasets that are transferred to the Sponsor or designee will contain the identifier only; subject names or any information which would make the subject identifiable will not be transferred. If a subject is rescreened and assigned a new subject number, both subject numbers for that individual will be linked.
- The subject must be informed that her personal study-related data will be used by the Sponsor or designee in accordance with local data protection law. The level of disclosure must also be explained to the subject.
- The subject must be informed that her medical records may be examined by Clinical Quality Assurance auditors or other authorized personnel appointed by the Sponsor or designee, by appropriate IRB/IEC members, and by inspectors from regulatory authorities.

### **10.1.5. Committees Structure**

Not applicable.

### **10.1.6. Posting Clinical Study Data**

Clinical study information will be posted on external registries and websites (eg, US National Institutes of Health's website [www.ClinicalTrials.gov](http://www.ClinicalTrials.gov) and European Clinical Trial Register) as per applicable regulatory requirements.

### 10.1.7. Data Quality Assurance

- All subject data relating to the study will be recorded on the eCRFs unless transmitted to the Sponsor or designee electronically (eg, laboratory data). The investigator is responsible for verifying that data entries are accurate and correct by physically or electronically signing the eCRF.
- The investigator must maintain accurate documentation (source data) that supports the information entered in the eCRF.
- The investigator must permit study-related monitoring, audits, IRB/IEC review, and regulatory agency inspections and provide direct access to source data documents.
- The Sponsor is responsible for the data management of this study including quality checking of the data. Management of clinical data will be performed in accordance with applicable Sponsor-approved standards and data cleaning procedures to ensure the integrity of the data.
- Study monitors will perform ongoing source data verification to confirm that data entered into the eCRF by authorized site personnel are accurate, complete, and verifiable from source documents; that the safety and rights of subjects are being protected; and that the study is being conducted in accordance with the currently approved protocol and any other study agreements, ICH GCP, and all applicable regulatory requirements.

#### 10.1.7.1. Study Site

All clinical study documentation must be retained by the investigator until at least 2 years after the last approval of a marketing application in an ICH region (ie, United States, Europe, or Japan) and until there are no pending or contemplated marketing applications in an ICH region; or, if no application is filed or if the application is not approved for such indication, until 2 years after the investigation is discontinued and regulatory authorities have been notified. Investigators may be required to retain documents longer if required by applicable regulatory requirements, by local regulations, or by an agreement with the Sponsor. The investigator must notify the Sponsor before destroying any clinical study records.

The study site and the record retainer should take measures in such a way that these records are not lost or abandoned during the designated period of preservation and that they are presented upon request.

#### 10.1.7.2. Institutional Review Board, Independent Ethics Committee, and Research Ethics Board (IRB/IEC/REB)

The protocol, protocol amendments, informed consent form, Investigator's Brochure, and any other relevant materials, including accompanying material to be provided to the subject (eg, advertisements, subject information sheets, or descriptions of the study used to obtain informed consent) will be submitted by the investigator to an IRB/REB/IEC. Initial approval from the IRB/REB/IEC must be obtained before starting the study and should be documented in a letter to the investigator specifying the following:

- Protocol number
- Protocol version
- Protocol date
- Documents reviewed
- Date on which the committee met and granted the approval

Any amendments to the protocol will require IRB/REB/IEC approval before implementation of changes made to the study design, except for changes necessary to eliminate an immediate hazard to study subjects.

The investigator will be responsible for the following (and must retain applicable notices and records as above under Study Site):

- Providing written summaries of the status of the study to the IRB/REB/IEC's annually or more frequently in accordance with the requirements, policies, and procedures established by the IRB/REB/IEC
- Notifying the IRB/REB/IEC of serious adverse events or other significant safety findings as required by procedures established by the IRB/REB/IEC
- Notifying the IRB/REB/IEC when the study has been completed or when his/her individual study site has been closed

#### **10.1.8. Source Documents**

- Source documents provide evidence for the existence of the subject and substantiate the integrity of the data collected. Source documents are filed at the investigator's site.
- Data entered in the eCRF that are transcribed from source documents must be consistent with the source documents or the discrepancies must be explained. The investigator may need to request previous medical records or transfer records, depending on the study. Current medical records must be available during the site monitor's visit.
- The required source documents are:
  - Subject identification (name, date of birth, sex)
  - Documentation that the subject meets eligibility criteria, (eg, history, physical examination, and confirmation of diagnosis to support inclusion and exclusion criteria)
  - Participation in the study (including study number)
  - Study discussed and date of informed consent
  - Dates of all visits

- Documentation that protocol-defined procedures were performed
- Results of efficacy parameters, as required by the protocol
- Start and end date (including dose regimen) of study drug (drug dispensing and return should be documented as well)
- Record of all AEs and other safety parameters (start and end date, and causality and intensity as assigned by the investigator)
- Concomitant medication (including start and end date)
- Date of study completion and reason for early discontinuation, if applicable.

#### **10.1.9. Study and Site Closure**

The Sponsor designee reserves the right to close the study site or terminate the study at any time for any reason at the sole discretion of the Sponsor. Study sites will be closed upon study completion. A study site is considered closed when all required documents and study supplies have been collected, and a study-site closure visit has been performed.

The investigator may initiate study-site closure at any time, provided there is reasonable cause and sufficient notice is given in advance of the intended termination.

Reasons for the early closure of a study site by the Sponsor or investigator may include but are not limited to:

- Failure of the investigator to comply with the protocol, the requirements of the IRB/IEC/REB or local health authorities, the Sponsor's procedures, or GCP guidelines
- Inadequate recruitment of subjects by the investigator
- Discontinuation of further study drug development

As stated above in [Section 10.1.7](#), the investigator is responsible for notifying the IRB/IEC/REB upon closure of the site or completion of the study.

#### **10.1.10. Publication Policy**

- The Sponsor has proprietary interest in this study. Authorship and manuscript composition will reflect joint cooperation between multiple investigators and sites and Sponsor or designee personnel. Authorship will be established prior to the writing of the manuscript. As this study involves multiple centers, no individual publications will be allowed prior to completion of the final report of the multicenter study except as agreed with the Sponsor.
- The Sponsor will comply with the requirements for publication of study results. In accordance with standard editorial and ethical practice, the Sponsor will generally support publication of multicenter studies only in their entirety and not as individual site data.

### **10.1.11. Compliance with Protocol**

The investigator is responsible for compliance with the protocol at the investigational site. A representative of the Sponsor will make frequent contact with the investigator and his/her research staff and will conduct regular monitoring visits at the site to review subject and study drug accountability records for compliance with the protocol. Protocol deviations will be discussed with the investigator upon identification, and the investigator will document the deviation in the subject records and/or any applicable eCRF(s). Significant protocol deviations will be reported to the IRB/IEC/REB according to the IRB/IEC/REB's reporting requirements.

## **10.2. Appendix 2: Clinical Laboratory Tests**

The clinical laboratory tests to be performed are detailed in [Table 2](#). Subjects do not need to fast prior to laboratory testing. Refer to the Laboratory Manual for information on where testing should be performed (site, local laboratory, central laboratory).

A urine dipstick will be performed at the study site at scheduled visits as noted in the Schedule of Assessments ([Section 1.3](#)) and when a subject presents with symptoms of a UTI at Unscheduled Visits. If the urine dipstick is positive for leukocytes, nitrites, or blood cells, then a urinalysis and culture/sensitivity testing will be performed on the sample. The urinalysis should be performed at the central laboratory and the culture and sensitivity should be performed at the site's designated local laboratory.

**Table 2: Clinical Laboratory Tests**

| Hematology                   | Chemistry               | Urinalysis and Urine Culture/Sensitivity a                                     | Other                       |
|------------------------------|-------------------------|---|-----------------------------|
| Hematocrit                   | Albumin                 | Blood   | FSH b            |
| Hemoglobin                   | Alkaline phosphatase    | Glucose   | Urine cytology d |
| Platelet count               | ALT                     | Protein   |                             |
| WBC (total and differential) | AST                     | Specific gravity  |                             |
| RBC                          | Bicarbonate             | Ketones   |                             |
|                              | Calcium                 | Occult blood  |                             |
|                              | Chloride                | Leukocyte esterase  |                             |
|                              | Creatinine c | Nitrite   |                             |
|                              | Glucose (non-fasting)   | Bilirubin   |                             |
|                              | Potassium               | Urobilinogen  |                             |
|                              | Sodium                  | Microscopic exam if positive for protein (RBCs, WBCs, epithelial cells, bacteria, yeast)  |                             |
|                              | Blood urea nitrogen     | pH  |                             |
|                              |                         | Color   |                             |
|                              |                         | Appearance  |                             |
|                              |                         | Culture/sensitivity: Culture, quantitation, isolation, identification, and susceptibility |                             |

ALT = alanine aminotransferase; AST = aspartate aminotransferase; RBC = red blood cell count; WBC = white blood cell count

a A sample for urinalysis and urine culture/sensitivity will be sent to the laboratory only if the urine dipstick performed at the site is positive for the presence of leukocytes, nitrites, or blood cells.

b Follicle stimulating hormone testing may be performed at screening to confirm postmenopausal status

c estimated glomerular filtration rate will be calculated and reported by the laboratory.

d at Screening only

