#### **8.4.6. Clinical Safety Laboratory Assessments**

All protocol-defined laboratory assessments must be conducted in accordance with the laboratory manual and the Schedule of Assessments ([Section 1.3](#)). See [Section 10.2](#) for the list of clinical laboratory tests to be performed and the Schedule of Assessments for the timing and frequency. Repeat or unscheduled samples may be taken for safety reasons or for technical issues with the samples.

The clinical significance of test results will be evaluated as follows:

- At screening, the investigator or physician subinvestigator will assess the clinical significance of any values outside the reference ranges provided by the laboratory, and subjects with abnormalities judged to be clinically significant will be excluded from the study.
- The investigator or physician subinvestigator must review the laboratory report, document this review, and record any clinically relevant changes occurring during the study in the AE section of the eCRF. The laboratory reports must be filed with the source documents. Laboratory abnormalities associated with the underlying disease are not considered clinically significant unless judged by the investigator to have worsened or be more severe than expected for the subject's condition.
- All laboratory tests with values considered clinically significant during participation in the study should be repeated until the values return to normal or baseline or are no longer considered clinically significant by the investigator or Sponsor's designated Medical Monitor.
  - If such values do not return to normal/baseline within a period of time judged reasonable by the investigator, the etiology should be identified and the Sponsor's designated Medical Monitor notified.
  - If laboratory values from nonprotocol specified laboratory assessments performed at the institution's local laboratory require a change in subject management or are considered clinically significant by the investigator (eg, SAE or AE or dose modification), then the results must be recorded in the eCRF.

A urine dipstick will be performed at the study site at scheduled visits as noted in the Schedule of Assessments ([Section 1.3](#)) and when a subject presents with symptoms of a UTI at Unscheduled

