Visits. If the urine dipstick is positive for leukocytes, nitrites, or blood cells, then a urinalysis and culture/sensitivity testing will be performed on the sample. The urinalysis should be performed at the central laboratory and the culture and sensitivity should be performed at the site's designated local laboratory.

If positive for nitrites and/or leukocyte esterase, indicating a possible infection, the subject should be treated with antibiotics per the clinical judgment of the investigator and in accordance with local site practice. Urine analysis, urine culture and sensitivity testing (performed from a sample collected on the same day as the dipstick) will be used to confirm the presence or absence of a UTI. If UTI is present, sensitivity testing will provide additional information to the investigator regarding pathogen susceptibility to the antibiotic selected for treatment based on the positive dipstick.

- Screening urine dipstick reagent strip test results: If positive, the screening and randomization period can be extended to a total maximum of 35 days prior to randomization) in order to accommodate the additional time required for antibiotic treatment. Some of the screening procedures may be repeated, as deemed clinically necessary, at the discretion of the investigator (eg, repeat the Screening Bladder Diary if subject had a symptomatic UTI during initial diary collection).
- Day 1 (treatment administration) urine dipstick reagent strip test results: Subjects with a dipstick positive for nitrites and/or leukocyte esterase on Day 1 (Visit 3) do not meet “day of treatment criteria” and therefore must not receive study treatment. The subject should be treated with antibiotics per the clinical judgment of the investigator and in accordance with local site practice and may then return for a rescheduled treatment Day 1 Visit within 10 days (but within a total maximum of 35 days of starting screening procedures). If the dipstick obtained at the rescheduled Day 1/treatment administration visit is negative for nitrites and leukocyte esterase and all “day of treatment criteria” are fulfilled, the subject can be treated.

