### **8.5.6. Adverse Events of Special Interest**

Selected nonserious and SAEs will be reported as AESIs. AESIs that also meet the definition of an SAE must be reported as described in [Section 10.3](#).

AESIs for this study include:

- Adverse events consistent with urinary retention
  - An AE of urinary retention should only be recorded when a subject has a raised PVR that requires intervention with CIC or temporary placement of a urinary catheter according to the following criteria:
    - a) subject has a PVR of  $\geq 350$  mL (regardless of symptoms), OR
    - b) subject has a PVR  $\geq 200$  mL and  $< 350$  mL and the subject reports associated symptoms, ie, sensation of bladder fullness or inability to void despite persistent effort, that in the investigator's opinion require CIC.

Note: An AE of residual urine volume should be recorded if, in the investigator's opinion, the raised PVR is clinically significant but does not fulfill the above definition for urinary retention.

- Adverse events suggestive of cystitis or UTI
  - An AE of UTI will be recorded if both the following criteria are fulfilled, regardless of subject symptoms:
    - a) a positive urine culture result with a bacteriuria count of  $\geq 10^5$  CFU/mL (ie,  $100 \times 10^3$  CFU/mL)
    - b) leukocyturia of  $\geq 5$  /hpf

If a subject meets the criteria for the definition of a UTI, the investigator will record whether the UTI was "symptomatic" or "asymptomatic" on the AE eCRF.

Note: If urinalysis/culture results are reported which, in the opinion of the investigator, are considered clinically significant but do not fulfill the above definition of a UTI, the findings should be recorded as AEs (eg, bacteriuria, leukocyturia).

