Except for all TEAEs which will be summarized by SOC and PT, the incidence of all other TEAEs by PT will be presented for the following in descending frequency based on the incidence of all subjects treated with URO-902.

- All TEAEs by SOC and PT;
- All TEAEs
- Treatment-related TEAEs (i.e., Possibly Related or Probably Related);
- All TEAEs by PT, and maximum severity (where the maximum intensity per subject will be counted at each level of summarization);
- TEAEs with Grade ≥ 3 ;

- Treatment-related TEAEs with Grade ≥ 3 ;
- Serious TEAEs;
- Treatment-related serious TEAEs;
- Fatal TEAE;
- TEAEs leading to discontinuation from study;
- TEAE of Special Interest;
- Treatment-related TEAE of Special Interest;
- Non-fatal serious TEAE;

An AE is considered an AE of Special Interest if on the AE eCRF the answer to the item “Is this an AE of Special Interest?” is “Yes”. For specific criteria used to identify AEs of Special Interest refer to section 8.5.6 of the protocol.

Overall AE listing will include the treatment arm, start and stop dates/times of the AE, treatment dates/times, and treatment emergent status.

A Treatment related AE is defined as an AE for which the investigator classifies the AE as being “Possibly Related” or “Probably Related” to study treatment on Adverse Event eCRF. Missing relationship and severity (intensity) will be imputed per [Section 4.2.3](#).

Additional summary table will be provided for AEs that occurred on or after the study dose through 48 weeks after the study dose administration and after additional OAB medication was taken, or initiation of investigational agent, or surgical intervention.

The following additional listings will be provided:

- Listing of deaths
- Listing of SAEs
- Listing of TEAEs of Special Interest
- Listing of TEAEs leading to study discontinuation

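### Table 2 lists urine microscopy only when protein is positive, so it does not guarantee the leukocyte count that the UTI adverse-event definition requires

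*Protocol*

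**What the plan says.** **Definition (Protocol 8.5.6).** "An AE of UTI will be recorded if both the following criteria are fulfilled, regardless of subject symptoms". Criterion (a) is a culture of at least 10^5 CFU/mL. Criterion (b) is leukocyturia of at least 5 per high-power field (hpf). A Note adds that urinalysis or culture results "considered clinically significant but do not fulfill the above definition of a UTI, the findings should be recorded as AEs", with bacteriuria and leukocyturia as examples. The heading over this group of adverse events of special interest (AESIs) is wider than the two-criterion term: it covers events suggestive of cystitis or UTI.

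**Trigger for sending a sample (Protocol 8.4.6; also Schedule of Assessments footnote f, Section 10.2 and Table 2 footnote a).** "If the urine dipstick is positive for leukocytes, nitrites, or blood cells, then a urinalysis and culture/sensitivity testing will be performed on the sample". Section 8.4.6 says that these tests "will be used to confirm the presence or absence of a UTI".

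**Test list (Protocol 10.2, Table 2).** Under urinalysis: "Microscopic exam if positive for protein (RBCs, WBCs, epithelial cells, bacteria, yeast". Leukocyte esterase and nitrite are listed without a condition.

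**Laboratory manual and extra samples (Protocol 8.4.6, 10.2).** "All protocol-defined laboratory assessments must be conducted in accordance with the laboratory manual and the Schedule of Assessments". "Repeat or unscheduled samples may be taken for safety reasons or for technical issues with the samples". Section 10.2 says that the tests are set out in Table 2, and cites the manual for where testing is done.

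**SAP.** Section 7.2 takes AESIs from an item on the adverse-event eCRF and adds: "For specific criteria used to identify AEs of Special Interest refer to section 8.5.6 of the protocol". Section 7.3 puts central urinalysis in listings only. Section 4.2.3 in general imputes no missing safety data; its specific rules for adverse events cover relationship, severity and partial dates.

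**The concern.** The definition depends on a count that the test list makes conditional on something unrelated to it. Protein is not part of the UTI definition and is not one of the findings that send a sample to the laboratory. An event could therefore meet the culture threshold and still be kept out of the UTI term because a test was not run, not because the test was negative.

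UTI is one of only two AESI groups. Protocol 4.2 names UTI, as the protocol defines it, among the parameters to be closely monitored. At stake is whether the reported incidence of protocol-defined UTI means what a reader will take it to mean, and whether the same clinical picture appears under one preferred term or several in SAP Tables 14.3.1.2.1, 14.3.1.3.1 and 14.3.1.11.

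**Working it through.** The plan states no figure to reproduce here. The check sets the rules side by side.

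**Step 1. What criterion (b) needs.** A number of leukocytes per hpf is a microscopy result. The esterase and nitrite lines in Table 2 give no count per field. Criterion (a) raises no difficulty: culture is sent on the same trigger, and the two ways the protocol writes its threshold agree (10^5 = 100 × 10^3).

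**Step 2. Follow a dipstick-triggered sample with culture of at least 10^5 CFU/mL through the rules.**

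| Protein | Microscopy listed? | Criterion (b) | Result under 8.5.6 |
|---|---|---|---|
| Positive | Yes | Count of 5/hpf or more | UTI |
| Positive | Yes | Count below 5/hpf | Not UTI; Note applies |
| Negative | No | No result | Both criteria not shown to be met; Note applies |

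The second and third rows end in the same place for different reasons. In one, leukocyturia was looked for and not found at the threshold. In the other, it was not measured. No sentence in either document separates them.

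**Step 3. What the Note changes.** The UTI rule applies regardless of symptoms. The Note applies only if the investigator finds the result clinically significant. So an infection that would have met both criteria can move from a rule that requires recording to one that depends on judgement, and the term changes to one such as bacteriuria.

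**Step 4. Does the SAP repair it?** No. It identifies AESIs from the eCRF item, refers back to Section 8.5.6 for the criteria, does not derive UTI from laboratory data and has no rule for a missing count.

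**Step 5. Size.** The documents give no rate of dipstick-positive, culture-positive or protein-negative urine. They show only where the gap can arise: four scheduled post-treatment dipsticks per subject (Weeks 2, 6, 12 and 24), plus unscheduled visits for UTI symptoms and the extra follow-up around elevated residual volume or catheterization.

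For scale only, take an active arm of n = 26 (Protocol 4.1) and two assumed quantities: r, the share of subjects with an infection that would meet both criteria if measured, and q, the share of those whose sample gets microscopy. Counting one infection per subject, expected infections are n × r, those classifiable as UTI are n × r × q, and those not classifiable are n × r × (1 − q).

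| r (assumed) | n × r | Classifiable, q = 25% | q = 50% | q = 75% | q = 100% |
|---|---|---|---|---|---|
| 5% | 1.3 | 0.33 | 0.65 | 0.98 | 1.3 |
| 10% | 2.6 | 0.65 | 1.3 | 1.95 | 2.6 |
| 20% | 5.2 | 1.3 | 2.6 | 3.9 | 5.2 |

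Over this grid, the number not classifiable as UTI runs from 0 (q = 100%) to 5.2 − 1.3 = 3.9. The range follows entirely from the assumptions and is not an estimate for this trial.

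**The case against.** **A missing count does have a destination.** Read literally, an event without a count does not fulfil both criteria, so the Note governs it. This stands. A reader might infer that such events have no classification, or drop out of the adverse-event data. The documents do not support that: a clinically significant finding is still recorded, under another term. Only a result judged not clinically significant could go unrecorded. What is missing is narrower: a distinction between a count not done and a low one.

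**The AESI table need not lose the event.** The AESI heading is wider than the UTI term, and flagging is by eCRF item. This also stands. One might infer that Table 14.3.1.11 must understate the AESI group, but a bacteriuria event can be flagged and appear there. What remains is a different preferred term and flagging that may vary between sites.

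**The laboratory manual may order microscopy on every sample, and the count can come from elsewhere.** The first is possible, and the loss would then be zero. It is not a full answer, because Section 10.2 makes Table 2 the list of tests and cites the manual for location; if the manual differs, Table 2 is wrong. Repeat samples are allowed, and Section 8.4.6 has local-laboratory results outside the protocol entered in the eCRF when they are clinically significant or change management. Both routes are discretionary and do not guarantee a count.

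**Little depends on it.** Antibiotic treatment of a possible infection and the Day 1 criteria do not wait for microscopy, safety analysis is descriptive, and the same rule applies in every arm under blinding. All fair. A reader might still infer a bias towards one arm, or a compromised dose-escalation review. Neither is supported: nothing suggests that protein status differs by arm, and the DSMB reviews unblinded Cohort 1 safety data up to Week 6, not only events coded as UTI; its charter was not available.

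**Conclusion.** The point holds as an internal inconsistency. Table 2 does not secure the count that Section 8.5.6 makes necessary, and a culture-positive, protein-negative urine cannot meet criterion (b) from the listed tests. The consequence is that the incidence of protocol-defined UTI may be understated or divided between preferred terms, with no way to tell from the tables whether leukocyturia was absent or unmeasured.

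The size is unknown and may be zero. The conclusion assumes that the Table 2 line is applied as written and that no discretionary count is obtained. It does not extend to subject treatment, to the efficacy analyses or to a difference between arms. It should be corrected because UTI is one of two AESI groups and the arms are small enough for a few reclassified events to show, but it does not put the trial's conclusions in doubt.

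**What to change.** 1. Reconcile Table 2 with Section 8.5.6, so that microscopy with a leukocyte count per hpf is reported on every urinalysis sent after a positive dipstick, without the protein condition. If the laboratory manual already requires this, correct the Table 2 line to match.
2. State in Section 8.5.6 or SAP 7.2 how an event that meets criterion (a) but has no count is tabulated, separately from one with a count below 5/hpf, and whether it is flagged as an AESI.

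The cost is one table line, one or two sentences of text and a laboratory charge for microscopy on urine already collected. The documents give no price; the charge should be small. No extra visit or sample is needed.
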